4.2 Exclusion criteria

Patients/subjects fulfilling any of the following criteria are not eligible for inclusion in this study. No additional exclusions may be applied by the investigator, in order to ensure that the study population will be representative of all eligible patients/subjects.

1. Use of other investigational drugs within 5 half-lives of enrollment, or within 30 days, whichever is longer.
2. History of hypersensitivity to any of the study drugs or its excipients or to drugs of similar chemical classes.
3. History or current diagnosis of ECG abnormalities indicating significant risk of safety for patients/subjects participating in the study such as:
 - Concomitant clinically significant cardiac arrhythmias, e.g., sustained ventricular tachycardia, and clinically significant second or third degree atrio-ventricular block without a pacemaker
 - History of familial long QT syndrome or known family history of Torsades de Pointes
4. Patients/subjects taking medications prohibited by the protocol (see [Section 5.5.8](#))
5. History of malignancy of any organ system (other than localized basal cell carcinoma of the skin or *in situ* cervical cancer), treated or untreated, within the past 5 years, regardless of whether there is evidence of local recurrence or metastases.
6. Pregnant or nursing (lactating) women
7. Women of child-bearing potential, defined as all women physiologically capable of becoming pregnant, unless they are using basic methods of contraception during dosing of investigational drug. Basic contraception methods include:
 - Total abstinence (when this is in line with the preferred and usual lifestyle of the subject. Periodic abstinence (e.g., calendar, ovulation, symptothermal, post-ovulation methods) and withdrawal are not acceptable methods of contraception

- Female sterilization (have had surgical bilateral oophorectomy with or without hysterectomy), total hysterectomy or tubal ligation at least six weeks before taking investigational drug. In case of oophorectomy alone, only when the reproductive status of the woman has been confirmed by follow up hormone level assessment
- Male sterilization (at least 6 m prior to screening). For female subjects on the study, the vasectomized male partner should be the sole partner for that subject
- Barrier methods of contraception: Condom or Occlusive cap (diaphragm or cervical/vault caps*). For United Kingdom: with spermicidal foam*/gel*/film*/cream*/ vaginal suppository*

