- Use of oral, (estrogen and progesterone), injected* or implanted* hormonal methods of contraception or other forms of hormonal contraception that have comparable efficacy (failure rate < 1%), for example hormone vaginal ring or transdermal hormone contraception* or placement of an intrauterine device or intrauterine system.
*: not approved in Japan, approved methods should be used.

In case of use of oral contraception women should have been stable on the same pill for a minimum of 3 months before taking investigational drug.

In case local regulations deviate from the contraception methods listed above, local regulations apply and will be described in the ICF

- Women are considered post-menopausal and not of child bearing potential if they have had 12 months of natural (spontaneous) amenorrhea with an appropriate clinical profile (e.g. age appropriate, history of vasomotor symptoms) or have had surgical bilateral oophorectomy (with or without hysterectomy), total hysterectomy or tubal ligation at least six weeks ago. In the case of oophorectomy alone, only when the reproductive status of the woman has been confirmed by follow up hormone level assessment is she considered not of child bearing potential.
8. Use of pharmacologically active weight-loss medications, GLP-1 agonists or SGLT2 inhibitors, within 3 months of Visit 1, or between Visit 1 and Visit 199/201 (randomization).
 9. Use of alpha glucosidase inhibitors within 3 months of Visit 1, or between Visit 1 and Visit 199/201 (randomization).
 10. Bariatric surgery.
 11. Lack of compliance with lifestyle intervention (defined as weight gain during Epoch 2) or with study medication (defined as < 80% study drug intake during Epoch 2), assessed at Visit 199/201 (randomization).
 12. History of ketoacidosis, lactic acidosis, or hyperosmolar coma, or any of these occurring between Visit 1 and Visit 199/201 (randomization).
 13. Symptomatic genital infection or UTI in the 4 weeks prior to Visit 1, or between Visit 1 and Visit 199/201 (randomization).
 14. GI disorders associated with chronic diarrhea.
 15. Congestive heart failure, New York Heart Association (NYHA) class III or IV.
 16. Myocardial infarction, stroke, surgery for heart disease, percutaneous coronary intervention in the 6 months prior to Visit 199/201 (randomization).

17. Unstable angina within 3 months of Visit 1, or between Visit 1 and Visit 199/201 (randomization).

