5.5.8 Prohibited medication

Use of following treatments is not allowed for entire study period:

- St. John's wort (strong CYP3A inducer)
- GLP-1 agonists
- SGLT2 inhibitors other than study medication
- Pharmacologically active weight-loss medication (including herbal medication)
- Alpha glucosidase inhibitor

Some medications or products must be used with caution:

- Use of grapefruit juice (strong inhibitor of CYP3A4) should be discouraged and its consumption must not happen within 2h of study medication intake.
- Use of antibiotic or antifungal medications that are strong inhibitors of CYP3A4 should be limited to 10 days during the study. Examples of such medications are clarithromycin, telithromycin, itraconazole, ketoconazole, voriconazole or posaconazole.
- Use of strong UGT inhibitors such as probenecid, valproic acid or mefenamic acid should be limited to 10 days during the study.

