2.4.2 Prior, concomitant and post therapies

Prior medications are defined as any drugs taken and stopped prior to the first dose of study medication. Concomitant medications for Epoch 3 are any medications given at least once between the day of first dose of double-blind study medication and the end of Epoch 3, including those which started pre-BL and continued into the treatment period.

The number and percentage of subjects receiving prior and concomitant medications will be summarized by treatment group and overall in the SAF in separate tables by therapeutic class and preferred term.

The number and percentage of subjects taking rescue medication, and duration of exposure to rescue medication during Epoch 3 will be summarized by treatment group.

The number and percentage of subjects on anti-diabetic medications at BL (randomization visit) will be summarized by treatment, baseline glycemic status, and medication types:

- Any anti-diabetic medication (insulin or OADs)
- Insulin
- OADs (used as single pills)
 - Metformin
 - SU - Sulfonylureas (including Sulfonamides)
 - AGIs
 - TZDs
 - DPP-4 inhibitors
- Combination of OADs
 - Phenformin + SU
 - Metformin + SU
 - Metformin + TZD
 - SU + TZD
 - Metformin + DPP-4i

- Metformin + AGI
- DPP-4i + TZD
- Other

The search criteria for the anti-diabetic medications by type are included in the appendix.

The use of prohibited medications, defined in Table 2-2 below, will also be summarized.

Table 2-2 Prohibited medication for reporting

Prohibited Medication	Drug code
Empagliflozin	07271601
Clarithromycin	00984601
Telithromycin	01548701
Itraconazole	00780701
Ketoconazole	00532501
Voriconazole	01510101
Posaconazole	01762801
Probenecid	00045101
Valproic Acid	00228501
Mefenamic Acid	00044201

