5.5 Rule of exclusion criteria of analysis sets

Table 5-2 Protocol deviations that cause subjects to be excluded

Deviation ID	Description of Deviation	Exclusion in Analyses
INCL01	No written informed consent obtained	Excluded from ENR, RUN, RAN, FAS, SAF, and PPS
TRT19	Withdrawal of the consent without discontinuation of study drug	Data collected after withdrawal of IC, excluded from FAS and SAF
TRT34	Mis-randomization	Excluded from FAS and PPS
INCL03	BMI outside range or missing	Excluded from PPS
INCL04	FPG and HbA1c not within range or missing	Excluded from PPS
INCL05	Waist circumference outside range or missing	Excluded from PPS
INCL06	VFA outside range or missing	Excluded from PPS
EXCL04	Use of prohibited medications	Excluded from PPS
EXCL05	History of malignancy	Excluded from PPS
EXCL06	Pregnant or nursing	Excluded from PPS
EXCL08	Use of pharmacologically active weight-loss medications	Excluded from PPS
EXCL10	Bariatric surgery	Excluded from PPS
EXCL20	Substances or alcohol abuse	Excluded from PPS
TRT06	Study treatment adjusted	Excluded from PPS
TRT11	Study treatment unmasked and subject not discontinued from the study	Excluded from PPS
TRT15	Use of prohibited medication and not discontinued from the study	Excluded from PPS
TRT22	Use of another investigational drug	Excluded from PPS
TRT35	Study medication taken after the morning meal	Excluded from PPS
TRT28	Misdispensed medication and taken by subject	Excluded from PPS
OTH01	Mis-randomization	Excluded from PPS

Table 5-3 Subject Classification

Analysis Set	PD ID that cause subjects to be excluded	Non-PD criteria that cause subjects to be excluded
ENR	INCL01	Not having informed consent; Not having screening epoch disposition page
RUN	INCL01	Not in ENR; Not having run-in epoch disposition page
RAN	INCL01	Not randomized
FAS	INCL01, TRT19, TRT34	Not in RAN;
PPS	INCL01, INCL03, INCL04, INCL05, INCL06, EXCL04, EXCL05, EXCL06, EXCL08, EXCL10, EXCL20, TRT06, TRT11, TRT15, TRT22, TRT35, TRT 28, TRT34, and OTH01	Not in FAS; Overall exposure on DB medication < 10 weeks unless premature discontinuation due to adverse events
SAF	INCL01, TRT19	No double-blind study drug taken

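### SAP Table 2-2 does not match the protocol's list of banned medications, so the planned prohibited-medication summary would count the wrong drugs

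*SAP*

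**What the plan says.** Protocol 5.5.8 holds two separate lists.

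- The first opens "Use of following treatments is not allowed for entire study period". It names five classes: alpha-glucosidase inhibitors, GLP-1 agonists, SGLT2 inhibitors apart from the study drug, weight-loss medication (herbal products included) and St. John's wort.
- The second opens "Some medications or products must be used with caution". It covers grapefruit juice, strong CYP3A4 inhibitors of the antibiotic or antifungal kind, and strong UGT inhibitors. The two inhibitor groups are each limited to 10 days.

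Protocol 5.6.2 makes use of a prohibited treatment a reason to stop study drug, and Protocol 9.3 promises a summary of prohibited-medication use.

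SAP 2.4.2 takes up that promise: "The use of prohibited medications, defined in Table 2-2 below, will also be summarized". Table 2-2 then gives ten drugs with drug codes, and its title marks it as a table for reporting. SAP Section 4, which records changes from the protocol's analyses, does not mention this list.

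PPS membership is dealt with elsewhere, in SAP 5.5. The PPS row of Table 5-3 reads in part "EXCL04, EXCL05, EXCL06, EXCL08, EXCL10, EXCL20, TRT06", and TRT15 follows later in the same row. Table 5-2 describes EXCL04 and TRT15 in terms of prohibited medication and gives no list of drugs.

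**The concern.** The prohibited-medication summary tells a reader of the report how often subjects took drugs that the protocol did not allow. Weight-loss medication, one of the banned classes, acts directly on the primary endpoint. A table with the wrong contents errs in both directions. A subject given five days of clarithromycin, within the 10-day limit, would be counted as a user of prohibited medication. A subject who started a GLP-1 agonist or an alpha-glucosidase inhibitor would not be counted there at all. A low count could then be read as good adherence to 5.5.8 when the table had not looked for most of what 5.5.8 bans.

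There is a second, softer worry. Table 2-2 is the only drug-level definition of prohibited medication in the SAP. A programmer deriving EXCL04 or TRT15 might reuse it.

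**Working it through.** The plan gives no statistical figure on this point, so the check is a comparison of lists.

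**Step 1: Table 2-2 against Protocol 5.5.8**

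| Group in Protocol 5.5.8 | Status there | Entries in SAP Table 2-2 |
|---|---|---|
| Alpha-glucosidase inhibitors | banned | 0 |
| GLP-1 agonists | banned | 0 |
| SGLT2 inhibitors other than study drug | banned | 1 (empagliflozin) |
| Weight-loss medication | banned | 0 |
| St. John's wort | banned | 0 |
| Strong CYP3A4 inhibitors | caution, up to 10 days | 6 (two antibiotics, four antifungals) |
| Strong UGT inhibitors | caution, up to 10 days | 3 |
| Grapefruit juice | caution | 0 |

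The entries add up to 1 + 6 + 3 = 10. Of these, 6 + 3 = 9 (9/10 = 90%) are caution-list drugs. Of the five banned classes, 5 − 1 = 4 have no entry (4/5 = 80%), and the fifth is represented by one drug. The nine inhibitors in Table 2-2 are the same nine that 5.5.8 gives as examples of drugs for cautious use.

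**Step 2: are the banned drugs reported anywhere else?** Yes. SAP 2.4.2 also tabulates all prior and concomitant medications by therapeutic class and preferred term, and alpha-glucosidase inhibitors have their own row in the baseline anti-diabetic summary. SAP Table 5-4 already holds search codes for three of the banned classes: A10BF (alpha-glucosidase inhibitors), A10BJ (GLP-1 analogues) and A10BK (SGLT2 inhibitors). The error is confined to the table that claims to isolate prohibited use.

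**Step 3: does Table 2-2 decide who is in the PPS?** Nothing in the SAP says so. Tables 5-2 and 5-3 do not cite it. The EXCL numbers follow the protocol's criterion numbers (05 malignancy, 06 pregnancy or nursing, 10 bariatric surgery, 20 substance or alcohol abuse). EXCL04 is therefore Protocol 4.2 criterion 4, "Patients/subjects taking medications prohibited by the protocol", which points to 5.5.8. EXCL08 corresponds to criterion 8, which names GLP-1 agonists and SGLT2 inhibitors as well as weight-loss drugs, although the short label in Table 5-2 mentions only the last.

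**Step 4: which eligibility criteria are PPS codes?** Six of the 34 exclusion criteria are (4, 5, 6, 8, 10, 20), so 34 − 6 = 28 are not. Criteria 9 and 11 are among the 28.

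**The case against.** The best defence is that Table 2-2 is a reporting aid and nothing more. The general medication tables show every drug taken. The nine inhibitors are also reasonable to monitor: 5.5.8 limits them to 10 days, and criterion 23 bars their chronic use at entry, so prolonged use would be a real departure. This stands as far as it goes. It does not rescue the table, which calls these drugs prohibited with no filter on duration and leaves out most of what the protocol does prohibit.

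Three stronger readings are tempting, and the documents do not support them.

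- *A reader might infer that the PPS removes the wrong patients.* As Step 3 shows, EXCL04 leads back to 5.5.8 and so reaches current use of alpha-glucosidase inhibitors and GLP-1 agonists. TRT15 covers prohibited medication where the subject was not discontinued. Reuse of Table 2-2 for these codes is a risk, not something the SAP states.
- *A reader might infer that users of banned drugs go unreported.* They would be missing from one summary, but present in the general tables (Step 2).
- *A reader might infer that leaving EXCL09 and EXCL11 off the PPS list is an error.* SAP 2.2 limits deviation-based PPS exclusions to major deviations that affect the primary endpoint analysis, and most eligibility criteria are not coded. For EXCL09, what may escape EXCL04 is alpha-glucosidase inhibitor use in the three months before Visit 1 that stopped before entry. For EXCL11, the criterion begins "Lack of compliance with lifestyle intervention (defined as weight gain during Epoch 2) or with study medication" and concerns the placebo run-in, while the endpoint is measured from a baseline at or before randomization. Because criterion 11 is about weight, there is a fair case for listing it. The SAP does not say whether the mis-randomization codes would catch such a subject. Whether to list it is still a judgement for the sponsor.

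**Conclusion.** The mismatch between SAP Table 2-2 and Protocol 5.5.8 is established: nine of ten entries are not banned drugs, and four of five banned classes are absent. The prohibited-medication summary would be wrong if run as written. For the PPS, the SAP leaves an ambiguity that invites misuse, not a proven error.

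The point is minor. The primary analysis is on the FAS and does not depend on any of these lists, and the PPS is a sensitivity set (SAP 2.5.4). The counts above are of list entries, not of subjects; the number of subjects affected cannot be derived from the documents. For scale only, one subject is 1/30 = 3.3% of a planned arm of 30, or 1/20 = 5% of a planned arm of 20.

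The conclusion assumes that the SAP is programmed as written, and that 5.5.8 is the governing list because the SAP declares no departure from it. It takes no view on which drugs ought to be banned or limited.

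**What to change.** Before database lock:

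1. Replace Table 2-2 with the banned list in Protocol 5.5.8. Use the Table 5-4 codes A10BF, A10BJ and A10BK, leave out study drug, and add codes for weight-loss medication and St. John's wort. Check that combination products with a banned component are caught, since SAP 2.4.2 itself has a row for metformin with an alpha-glucosidase inhibitor.
2. Report strong CYP3A4 and UGT inhibitors in a separate table, with use over 10 days flagged.
3. Add one sentence to SAP 5.5 saying that EXCL04 and TRT15 are judged against Protocol 5.5.8 and not against Table 2-2.
4. Optionally, consider adding EXCL09 and EXCL11 to Tables 5-2 and 5-3, or note why they are left out. SAP 2.2 requires major deviations to be settled before unblinding, so the decision belongs in the same revision.

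The cost is a short SAP edit and a revised code list for one summary table. Items 1 to 3 leave PPS membership as the SAP now implies it; item 4, if adopted, might remove a few subjects from the PPS.

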5.6 Anti-diabetic medications search criteria

The documents attached below contain the search criteria of anti-diabetic medications for reporting.

Table 5-4 Search criteria for anti-diabetic medications by type

Category	Type	ATC code or drug code
Insulin	All insulin A10A	A10A (all insulin), and within this group: A10AB, A10AC, A10AD, A10AE and A10AF
OADs – used as single pills	Metformin	A10BA Biguanides
	SU	A10BB Sulfonylureas
		A10BC Sulfonamides (heterocyclic)
	AGIs	A10BF Alpha glucosidase inhibitors
	TZDs	A10BG Thiazolidinediones
	DPP-4i	A10BH Dipeptidyl peptidase 4 (DPP-4) inhibitors
Combinations of OADs	GLP-1 analogues	A10BJ Glucagon-like peptide-1 (GLP-1) analogues
	SGLT2i	A10BK Sodium-glucose co-transporter 2 (SGLT2) inhibitors
Other		See the slide attached below.
Category	Type	A10BX Other ATC code or drug code

Classification of
non-insulin drugs

6 Reference

Matsuo S, et al. (2009) Revised equations for estimated GFR from serum creatinine in Japan. *American Journal of Kidney Disease*; 53(6):982-92

